**SYNOPSIS**

Title of Study	Safety and efficacy of concentrated autologous concentrated bone marrow aspirate (BMAC) in preventing wound complications in amputations
Objectives	

• Determine the safety and explore efficacy of BMAC in preventing wound complications in amputations.

• Characterize the host tissue response to, paracrine activity of, and fate of transplanted BMAC.

• Determine the effects of chronic limb ischemia and diabetes on nerve function and to assess the effects of mesenchymal stem cell administration on their function.

Planned Number of Subjects and Duration of Involvement	12 patients, 12 month follow up period
Patient Population	Critical limb ischemia (CLI) patients scheduled for amputation
Investigational Product Name	Concentrated autologous bone marrow aspirate (BMAC)
Methodology Overview	
This is an open label pilot trial.
 
Up to twelve (12) patients scheduled for amputation will receive bone marrow cells concentrated (BMAC) via the BioCue™ Platelet Concentration Kit device injected IM at 25 sites in the leg proximal to the amputation in the index limb to prevent ischemic wound complications after surgery. BMAC will be injected into the anterior tibialis muscle (ATM) below the point of amputation for analytical purposes. Patients will be scheduled for amputation at Day 7 post injection. Safety will be evaluated by review of treatment related adverse events (AE) during the 12-month follow-up period. In subjects undergoing BKA, we will compare rates of wound complications and conversion from BKA to AKA to historical controls at our institution to assess trends in therapeutic efficacy.
 
Patients will undergo amputation and injection sites will be harvested from the ATM at that time. Immunohistochemical staining (IHC) will determine capillary density and local host immune responses. Angiogenic and inflammatory cytokines will be quantified using a multiplex array system and quantitative polymerase chain reaction (PCR).

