## **3 STUDY OBJECTIVES**

The principal objectives of this study are as follows:

**Determine the safety and explore efficacy of BMAC in preventing wound complications in amputations.** In a Phase I trial, BMAC (up to 5 mL) will be injected into the ATM below the point of amputation in the index limb in an area of approximately 3 x 10 x 3 cm. At the same time, BMAC (1 mL) will be injected at approximately 25 sites in the proximal leg to promote tissue perfusion before

amputation ([Figure 4](#)). Patients will be scheduled for amputation at approximately one week post injection. Safety will be evaluated by review of treatment related Adverse Events during the 12-month follow-up period. Efficacy will be assessed by rates of wound complications and revision of amputation to historical controls at our institution to assess trends in therapeutic efficacy.

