### **9.3 Planned Analyses**

The clinical study report will contain only summary data analyses reflecting safety profiles, and summary data analyses of efficacy. All patient data will remain coded during analyses to maintain patient confidentiality.

The data management center for this trial will be at the CTSI, or a Data Monitoring Committee (DMC) will be appointed by the Principal Investigator. We will use a web-based HIPAA compliant online system for data entry and data management, as we are currently doing in our current clinical trials. Data will be collected from each enrolled patient using a comprehensive case report form and uploaded into a specifically designed database in the OnCore Enterprise Clinical Trial Management System and VA REDCap system. All the data will be analyzed and generated using SAS.

**Safety Assessment.** Primary attention will focus on the safety of the administration of BMAC as measured by treatment-related AEs. Treatment-related AEs will be categorized overlapping systems and severities. Three categories of systems are cardiovascular, respiratory, or infectious. Two categories of severity will be serious adverse (SAE) and major adverse cardiac events (MACE). For completeness, instances of AEs may appear in more than one category. Within each of these categories AEs will be listed in descending order of frequency for the treatment group. In addition, for each category, the sum and difference between the two routes of delivery of the proportions will be reported as percent incidence. Binomial confidence Intervals at the 95% confidence level and *p*-values for these 3 groups will be calculated. Since previous trials have not reported AEs with BMAC treatment, confidence intervals will be generated by the method of the Wilson Score Interval because they are robust, with good coverage probability even for small number of trials and are not degenerate near zero. These intervals will be used to summarize the data rather than as any formal inferential statement and to assist the Data Monitoring Board in their deliberations. No adjustment for multiplicity will be made.

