**Exploratory Efficacy.** Continuous confidence intervals at the 95% level will be constructed to explore the effect of administration of BMAC on the composite endpoint at 6-months of death, revision of amputation and gangrene, and will be compared to historical cohorts at our institution. The null hypothesis of no change will be rejected if the pairwise confidence intervals does not include zero. The critical levels for the multiplicity adjustment will be determined by simple Monte Carlo simulation.

Quantities over time of BMAC will be fit to an exponential decay curve using a residual pseudo-likelihood procedure and cell half-life ( $\lambda$ ) will be estimated. Binomial confidence Intervals at the 95% confidence level and *p*-values for these four groups after BMAC transplantation will be calculated for the presence or absence of MHC expression and SDF-1 activation. Continuous confidence intervals at the 95% level will be constructed to explore the differences among the time-tiered administration of BMAC for (1) the CD34+CD133+ pro-angiogenic hematopoietic cells recruitment of HIF-1 $\alpha$ /SDF-1/CXCR4 to ischemic muscle, (2) the quantify of capillary density in muscle fibers using hematoxylin phloxin saffron and CD31 counts, (3) VEGF-A,C,D, hepatocyte growth factor, angiopoietin-1 to characterize angiogenic cytokine expression, (4) percent coverage, fiber diameter and cross-sectional area to examine changes in morphology. The correlation between capillary density (CD31 counts) with tissue perfusion (ICA) for each time point will be estimated by Spearman's rank coefficient.

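### Section 9.3 judges a yes/no composite in about 12 subjects by an unnamed 'continuous' 95% interval, and the efficacy comparison differs from section to section

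*Combined protocol and SAP*

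**What the plan says.** **Interval and rule.** In the Exploratory Efficacy part of Section 9.3: "Continuous confidence intervals at the 95% level will be constructed to explore the effect of administration of BMAC on the composite endpoint at 6-months". The components are death, amputation revision and gangrene, and the comparator is the institution's historical cohorts. No formula is given. The rule follows: "The null hypothesis of no change will be rejected if the pairwise confidence intervals does not include zero". Then: "The critical levels for the multiplicity adjustment will be determined by simple Monte Carlo simulation".

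**Other intervals in Section 9.3.** Binomial intervals "will be calculated for the presence or absence of MHC expression and SDF-1 activation". For adverse events the Safety Assessment paragraph chooses the Wilson score interval, as robust, "with good coverage probability even for small number of trials and are not degenerate near zero", and adds: "These intervals will be used to summarize the data rather than as any formal inferential statement".

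**What efficacy is compared.**
- Synopsis: "In subjects undergoing BKA, we will compare rates of wound complications and conversion from BKA to AKA to historical controls at our institution".
- Section 3, and the same sentence in Section 7.1: "Efficacy will be assessed by rates of wound complications and revision of amputation to historical controls".
- Section 7.1 also has revision rates at 12 months set against historical controls, and a week-52 call to assess primary endpoints. Table 4 schedules the gangrene and revision evaluations at that call.
- Section 9.3: the 6-month composite.

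Section 9.1 states that the study is not powered for efficacy.

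**The concern.** Each subject either has a composite event by 6 months or does not, so the summary is a proportion. Elsewhere in the same part of Section 9.3, 'continuous' intervals are for measured tissue quantities such as capillary density, and yes/no tissue data get binomial intervals. A literal reader could therefore apply an unpooled normal, Welch t or pooled t interval to 0/1 data. With about 12 subjects and possibly no events, the first two of these degenerate in the way that the safety paragraph guards against by choosing Wilson.

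At stake is whether the reported 95% interval means what it says and, at a few outcomes, whether 'no change' is rejected because of the formula and not the data. In addition, with several unreconciled comparisons, the endpoint, time point and population can be chosen after the data are seen.

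**Working it through.** **Inputs.** n = 12 (Section 5.1.1); 95%, taken as two-sided (Section 9.3). The documents give neither the historical composite rate nor the cohort size, so there is no planned figure to reproduce. The nearest rate is in Section 1: BKA-to-AKA conversion of up to 19%, which is not the composite. I assume historical rates of 19-50% and 30, 50, 100, 200, 300 or 500 controls.

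**Formulas.** With d = p1 - p2 (BMAC minus historical):
- Unpooled normal: d ± 1.960 × √[p1(1-p1)/n + p2(1-p2)/N].
- Newcombe-Wilson, from the Wilson limits (l, u) of each proportion: lower = d - √[(p1-l1)² + (u2-p2)²]; upper = d + √[(u1-p1)² + (p2-l2)²].

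**Step 1: 0/12 against 19/100 (assumed).** d = -0.190.
- Unpooled: the treated group contributes zero variance. SE = √(0.19×0.81/100) = 0.0392, so the interval is -26.7 to -11.3 points and excludes zero.
- Newcombe-Wilson: the Wilson limits are 0 to 0.242 and 0.125 to 0.278. Lower = -0.190 - 0.088 = -0.278. Upper = -0.190 + √(0.242² + 0.065²) = +0.061. The interval is -27.8 to +6.1 and includes zero.
- Welch t (-26.8 to -11.2) excludes zero; pooled t (-41.6 to +3.6) does not.

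**Step 2: 1/12 against 30/100 (assumed).** d = -0.217.
- Unpooled: SE = √(0.00637 + 0.00210) = 0.0920, so -39.7 to -3.6. Welch t: -41.6 to -1.7. Both exclude zero.
- Newcombe-Wilson: -33.4 to +6.6. Pooled t: -48.7 to +5.4. Neither excludes zero.

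**Step 3: how often the interval covers the true difference.** Exact binomial enumeration over all outcomes; ranges are over the six cohort sizes.

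| Historical rate | Unpooled, equal rates | Newcombe-Wilson, equal rates |
|---|---|---|
| 19% | 89.6-90.6% | 95.6-96.2% |
| 30% | 89.1-92.7% | 94.5-95.3% |
| 40% | 89.5-92.8% | 94.6-95.3% |
| 50% | 90.6-92.7% | 94.3-95.6% |

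If BMAC truly halves a 19% rate, unpooled coverage is 69.4-92.4% and Newcombe-Wilson 95.5-96.2%. The low end has a simple cause. At a true 9.5% rate, 0/12 occurs with probability 0.905^12 = 30%. With 500 controls at 19%, the unpooled interval is then -19.0 ± 3.4 points, which misses the true -9.5.

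**Step 4: how often the formula matters for the verdict.** With equal true rates and unadjusted limits, unpooled and Newcombe-Wilson disagree in 8.4-10.6% of trials at 19%, 3.2-7.9% at 30%, 1.8-5.8% at 40% and 1.7-5.0% at 50%.

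**Step 5: effect of the Monte Carlo levels.** Suppose they simulate the yes/no data at the true rate with 100 controls.
- 0/12 against 19/100 has |z| = 0.190/0.0392 = 4.84. The critical value is 4.69 at a two-sided 5% (rejects), 4.84 at 4% (not exceeded) and 5.16 at 2.5%, as for two comparisons (does not reject).
- 1/12 against 30/100 has |z| = 0.217/0.0920 = 2.35 against 2.46 at 5%, and does not reject.

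So a real multiplicity adjustment of this kind removes both unpooled rejections. Section 9.3 does not say whether this is what is simulated, or over how many comparisons.

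**Step 6: the efficacy comparisons side by side.** They differ in endpoint (wound complications, conversion, revision, composite), time point (12 months, 6 months, or none stated) and population (BKA subjects only, or all subjects). Section 9.3 gives no method for wound complications beyond a general promise of summary efficacy analyses. Conversion is covered at most as a form of revision inside the composite.

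**The case against.** The strongest case against has four parts.

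- **Critical values.** The opposite verdicts in Steps 1 and 2 use unadjusted limits, which Section 9.3 does not plan. This stands: Step 5 shows that they can vanish. A reader might infer that the plan as written will produce false claims of benefit. The documents do not support that, because the simulated levels are undefined. The coverage shortfall in Step 3 concerns the 95% interval itself and does not depend on the rejection rule.
- **The assumed rate.** Disagreement is greatest at 19%, a ceiling for conversion alone; a composite that adds death and gangrene may well be commoner. With exactly 50 events in 100 controls, the two formulas agree at every treated count. This stands for the verdicts. Unpooled coverage under equal rates is still only 90.6-92.7% at 50%.
- **Consequences.** A reader might infer that a rejection drives the Phase II design or the next dose study. It does not. The Phase II sentence in Section 3 sits under the tissue-response objective. Section 6.1.2 covers only the case of no evidence of efficacy and does not invoke the rule. The analysis is headed exploratory.
- **The 6-month clock.** A reader might see an open start date as a serious bias. Section 7.1 dates the visits through week 24 from amputation, and revision cannot precede amputation, so this is minor. What remains is a death in the week or so between injection and amputation: 1/12 if counted, 0/11 if dropped.

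The choice of Newcombe-Wilson is also partly preference. Miettinen-Nurminen would serve as well.

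**Conclusion.** The point holds in a limited form. Section 9.3 attaches an unnamed 'continuous' interval and a formal rejection rule to a yes/no outcome in about 12 subjects, against its own practice for other yes/no data. A common literal reading gives intervals that are too narrow: coverage of about 89-93% when rates are equal, and as low as 69% when a 19% rate is halved, against 94-96% for Newcombe-Wilson. At unadjusted critical values the formula decides the verdict at a few low counts; at most outcomes it makes no difference. The Monte Carlo levels could remove these unpooled rejections but are not specified well enough to tell. The mismatch between efficacy comparisons is a separate defect that needs no calculation.

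All sizes rest on assumed historical rates of 19-50% and 30-500 controls. Because the analysis is exploratory and no action is tied to a rejection, this should be corrected before the data are analysed, but it does not threaten the trial's safety objective.

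**What to change.** 1. In Section 9.3, name a binomial interval for the difference with good small-sample coverage. Newcombe-Wilson matches the Wilson choice for adverse events; Miettinen-Nurminen is also acceptable. If the comparator is a fixed historical rate, use Wilson or exact limits for the single proportion.
2. For this endpoint, drop the rejection sentence and the Monte Carlo levels, and reuse the safety paragraph's statement that the intervals are descriptive.
3. Before analysis, reconcile endpoint, time point and population across the Synopsis, Sections 3, 7.1 and 9.3 and Table 4. Name one main comparison; the sponsor chooses 6 or 12 months. Report the others, including wound complications, descriptively with the same interval.
4. Report deaths between injection and amputation separately, so that treated subjects are not silently dropped. Do not count gangrene present before amputation as an outcome event, since Table 3 admits patients who already have it.

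**Cost.** Wording in Section 9.3 and matching edits in the other places listed, with no new subjects or visits. The interval is wider: at 0/12 against 19/100, 6.1 + 27.8 = 33.9 points instead of 26.7 - 11.3 = 15.4. There is no formal efficacy verdict, which is consistent with Section 9.1.

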#### **6.1.2 Safety issues**

Safety of the BioCue™ device to concentrate BMA for the prevention of wound complications in amputation will be determined by review of treatment related adverse events (AE) and serious adverse events (SAE) during the study period of 12 months by the Data Safety Monitoring Board (DMSB) appointed by the Clinical and Translational Sciences Institute (CTSI) at the Indiana School of Medicine or Data Safety Committee (DMC) designated by the Principal Investigator.

The BMAC dose proposed in this trial was selected based on prior clinical trials. We may not see any evidence of efficacy in our composite endpoint, which may reflect an inadequate dose or sample size. In this case we would propose a future study exploring escalating doses of BMAC. In the instance of evolving infection, we would re-assess our inclusion/exclusion criteria and evaluate the contribution of pre-amputation procedures on the lower leg. Patients may request earlier amputation due to worsening rest pain or anxiety. Consideration for amputation sooner than one week post injections will be determined by the PI based on the severity of the subject's condition, so as to offer this research as an option to all eligible subjects.

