## **9 STATISTICAL METHODS**

### **9.1 Determination of Sample Size**

The study is not powered for efficacy in preventing wound complications of revision of amputation. The maximum number of tissue specimens we hope to collect will be twelve (12). Quantification of BioCue™, capillary density and cytokines will be compared between injection sites (between escalating doses and control) using a paired Student's t-test. Serum cytokine levels post BioCue™ injection will be compared to baseline levels using a paired Student's t-test.

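### Sections 9.1 and 9.3 plan half-life, dose, group, time-tier, route and ICA analyses that the readable single-cohort, single-harvest design does not support; the passages must be reconciled

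*Combined protocol and SAP*

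**What the plan says.** **Design text.** Section 4.1 describes a single-centre, open-label Phase I study of up to 12 patients and names no arms or cohorts. Section 2.2 allows intramuscular administration only. Section 6.1.3 places harvest, processing and administration in one procedure, and Section 7.1 has the ATM and the proximal leg injected together. The Synopsis schedules amputation at Day 7, and Section 7.1 at about one week. Section 7.1 retrieves the injected ATM sites at amputation. Section 3 names soleus muscle as the control tissue.

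**Analysis text.**
- Section 9.1: tissue quantities are "compared between injection sites (between escalating doses and control) using a paired" t-test. Section 6.1.2, discussing what to do if no efficacy is seen, says: "In this case we would propose a future study exploring escalating doses of BMAC".
- Section 9.3, safety: "the sum and difference between the two routes of delivery of the proportions will be reported as percent incidence", with binomial intervals and p-values "for these 3 groups will be calculated".
- Section 9.3, exploratory: "Quantities over time of BMAC will be fit to an exponential decay curve using a residual pseudo-likelihood procedure and cell half-life" is to be estimated. For MHC and SDF-1, intervals and p-values "for these four groups after BMAC transplantation will be calculated". Further intervals are to "explore the differences among the time-tiered administration of BMAC". "The correlation between capillary density (CD31 counts) with tissue perfusion (ICA) for each time point" is to be estimated by Spearman's coefficient.

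**The concern.** An analyst working from Sections 9.1 and 9.3 cannot tell which doses, routes, groups or times to compare, because the design sections do not supply them. The fate of the transplanted cells is a named objective in Section 3, and the half-life is the only quantity in Section 9.3 that measures their persistence over time. If it is attempted as written, it either yields no estimate or rests on the few patients amputated early for clinical reasons. The route contrast sits in the safety assessment, to which Section 9.3 gives primary attention and which is meant to assist the monitoring board. Subjects have already been treated under earlier protocol versions (Section 1). Levels chosen now, without a dated record, could therefore be chosen with data in view.

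**Working it through.** The plan gives no power or precision figure to reproduce. Section 9.1 says the study is not powered for efficacy and gives 12 as the maximum number of tissue specimens.

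**1. Half-life from tissue.** On the log scale the decay model is log q = log A − k·t, with two unknowns: starting quantity A and rate k. Half-life is ln 2 / k. With all 12 specimens at t = 7, every row of the design matrix is (1, −7), so the rank is 1 for 2 parameters. A and k cannot be separated, and more specimens or sites on the same day add identical rows. Two or more planned harvest times would give rank 2.

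**2. Half-life anchored on the injected quantity.** Taking the injected dose as time zero also gives rank 2 (t = 0 and t = 7). The plan does not state this anchor. It would leave two points per patient and no check of the exponential form. It also depends on the ATM volume, given as up to 5 mL in Section 3 and up to 3 mL in Section 7.1 and the Figure 4 text; these must be reconciled. With half-life = 7·ln 2 / ln(A/q), and assuming for illustration that the amount left at Day 7 is a given share of a 3 mL dose:

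| Amount left (assumed) | Half-life if 3 mL injected | Half-life if 5 mL injected |
|---|---|---|
| 10% of a 3 mL dose | 7 × 0.693 / ln(10) = 2.1 days | 7 × 0.693 / ln(16.7) = 1.7 days |
| 50% of a 3 mL dose | 7 × 0.693 / ln(2) = 7.0 days | 7 × 0.693 / ln(3.33) = 4.0 days |

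The remaining fractions are not in the documents. The table shows only that the answer moves with the starting quantity.

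**3. Half-life from unplanned early amputations.** Section 6.1.2 lets the severity of the patient's condition decide who is amputated before one week. Suppose those patients are harvested g days early and severity shifts their log count by δ. The fitted rate is then k + δ/g. Time and severity cannot be separated, and the documents give neither the size nor the sign of δ.

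**4. Other analysis factors against the design.**

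| Factor in Sections 9.1 and 9.3 | Readable design |
|---|---|
| Escalating doses | No dose levels; Section 6.1.2 places escalation in a future study |
| Four groups | Nothing in the text for it to refer to |
| Time-tiered administration | No tiers; one nominal interval of about seven days |
| ICA at each time point | ICA otherwise appears only in the abbreviation list; Table 4 schedules LEADs/TcPO2 |
| Two routes | Only intramuscular |
| Three groups (safety) | Ambiguous; the same paragraph lists three adverse-event systems |

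If the two routes mean ATM and proximal leg, every subject receives both at the same time. A local event can be placed at a site until amputation. A systemic event cannot be assigned to either.

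**The case against.** The strongest objection is that the missing levels may exist out of sight. Figure 3, titled as the scheduling scheme, and other figures in Section 7.1 are not visible. The tissue methods in Section 7.1 also refer to several time points without listing them. Some subjects were treated under protocol versions whose schedules are not shown. This stands. A reader might infer that the dose and time tiers never existed; the documents do not support that.

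Second, the half-life is not impossible in principle. Section 6.1.3 counts the cells in the device output and records viability and total delivery volume, so a time-zero quantity could be built. This stands in part. The plan does not say so, marker characterisation of the product is optional, and ATM-specific volume is not among the listed records.

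Third, a reader might infer that no harvest time is defined. One is: amputation, nominally Day 7. Only the additional times are missing. Nor does the text show that the three safety groups are undefined, since the three adverse-event systems are a likely meaning.

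Fourth, a reader might try to put a precision figure on the four groups by dividing 12 patients equally. The documents do not support that either: the groups could be sites within a patient.

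Finally, the board would not be left without usable tables. Section 9.3 already lists adverse events by category for the single treatment group and calls the intervals descriptive. That limits the harm but does not define the route contrast.

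**Conclusion.** The point holds as a conflict between the analysis text and the readable design. The decay fit is not identifiable from tissue taken on one nominal day (rank 1 of 2). Unplanned early amputation offers only an estimate confounded with severity. Escalating doses, four groups, time tiers and two routes have no readable levels, and the ICA correlation has no procedure behind it. The soleus comparison is unaffected, because its control is defined.

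The conclusion rests on two conditions: that the visible text is the whole design, and that harvest occurs at about Day 7 in all patients apart from clinical exceptions. If the hidden figures or earlier versions define tiers, the task becomes stating them and reconciling them with Day 7. The importance is modest: these analyses are exploratory or descriptive in an unpowered pilot, and the likely harm is an empty or misleading mechanistic result and one uninterpretable safety contrast.

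**What to change.** First check Figure 3, the Section 7.1 figures and the earlier protocol versions. If they define dose levels, groups, tiers, harvest times or ICA visits, state these in Sections 4 and 7 and Table 4, reconcile them with Day 7, and say which analysis uses which level.

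For whatever is not defined there:

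1. Delete the half-life, or report it only as a dose-anchored descriptive value with the time-zero quantity defined and measured and the ATM volumes reconciled. Do not fit it to unplanned variation in amputation day. List injection-to-harvest days for each patient.
2. Delete the escalating-dose, four-group, time-tier and ICA-correlation text.
3. Replace the route sum and difference with single-group n/N and a Wilson interval per adverse-event category. For 0 of 12 the upper limit is z²/(n + z²) = 3.84/15.84 = 24%. Local injection-site events may be listed by site up to amputation. State what the three groups are.
4. Report MHC and SDF-1 as single-group n/N with a 95% binomial interval. Report pro-angiogenic cell density, capillary density and muscle cytokines as paired ATM-minus-soleus differences with 95% confidence intervals, noting that muscle type also differs.
5. In the tissue methods of Section 7.1, say that injected ATM is harvested at amputation, and list the optional needle biopsies separately, since some may be taken at injection.
6. Date the change and declare whether tissue data had been seen.

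The cost is a document check and one amendment covering Sections 4, 7.1, 9.1 and 9.3 and Table 4. Where no tiers exist, the study gives up dose and time contrasts that it could not have estimated. Without a dose-anchored value, the fate objective becomes a description at one time.
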